## 9.7 CORE LABORATORIES

The NHLBI CT and Echocardiography Core Laboratories will analyze all imaging and compare post-procedure imaging with baseline (pre-procedure) imaging. Analysis will include but will not be limited to the following:

- Assessment of baseline eligibility
  - Likelihood of entrapment of Cardiac Implanted Electronic Devices (CIED) by the cerclage system
  - Suitability of coronary venous anatomy for the cerclage procedure
  - Geometry of likely cerclage trajectory
- Assessment of cerclage device post-implantation characteristics
  - Cerclage position
  - Cerclage integrity
  - Cerclage-related compression of underlying coronary arteries
  - Cerclage-related tricuspid valve dysfunction
- Assessment of impact of cerclage on heart function
  - Cardiac chamber size and function
  - Severity of mitral valve regurgitation
  - Impact of cerclage on function of non-target valve function (tricuspid and aortic)

## 9.8 DATA SAFETY MONITORING

A Data Safety and Monitoring Board (DSMB) appointed by the NHLBI Division of Intramural Research will monitor the safety of subjects in the study as described in the investigational plan, as required for interventional studies at NHLBI Division of Intramural Research. All members of the DSMB are unaffiliated

to the study. The NHLBI DSMB will review the protocol progress report at six-month intervals. The DSMB may recommend early termination of the study for considerations of safety and efficacy, using proposed Stopping Rules (section 9.9) as a guidance. Unanticipated Adverse Device Effects (UADEs) will be submitted to the DSMB following the same timelines as the IRB (See section 9.2.4).

In all cases of death or serious UADE, the sponsor and the NIH Principal Investigator will make a determination whether the event presents an unreasonable risk to the participating subjects. If this determination is affirmative, the clinical trial will be terminated within 5 working days after making that determination and not later than 15 working days after the sponsor first receives notice of the effect. [21 CFR 812.46]. All clinical sites will be notified of this action.

The IRB will review all Unanticipated Adverse Device Effects, and Unanticipated Problems, and may choose to suspend or terminate the protocol based on those findings. We believe this will protect subject safety. The IRB will review Serious Adverse Events and Serious Adverse Device Effects during continuing review.

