## 9.9 STOPPING RULES

The study will be monitored to ensure that the mortality within 30-days after the procedure does not substantially exceed an anticipated rate. We anticipate the rate of 30-day mortality is 10% or less and determine the stopping rule by a Bayesian approach . The stopping boundary is reached if the posterior probability that the 30-day mortality rate exceeds 10% is at least 85%. We take our prior distribution to be a beta distribution so that our prior clinical opinion is worth 20% of the weight we will place on the new data. This gives the prior parameters  $a = 0.6$ ,  $b = 5.4$ . Hence when we make decisions about stopping the study, the data from the study will dominate over the prior opinion.

The following table summarizes the threshold numbers for the stop rule boundary, which may lead to a recommendation to stop the study due to the excess 30-day mortality.

| Number of subjects | Stop if the number of deaths within 30 days reaches |
|--------------------|---|
| 2-5                | 2   |
| 6-12               | 3   |
| 13-20              | 4   |
| 21-28              | 5   |
| 28-30              | 6   |

We investigated the performance of the above stopping rule by a simulation study. In each simulation run, we generated a study with 15 independent Bernoulli trials, each with a true certain 30-day mortality, and compared these outcomes with the above stopping boundary to determine whether the study was stopped. We repeated the simulation 100,000 times and computed the proportion of stopped studies using the above stopping rule. The following table summarizes the performance of this stopping rule:

| True 30-day mortality rate             | 2.5% | 5%   | 10%  | 15% | 20%  | 25%  | 30% | 35% |
|--|------|------|------|-----|------|------|-----|-----|
| Proportion of Stopped Studies (%)      | 1    | 4    | 24   | 52  | 76   | 90   | 97  | 99  |
| Average number of subjects (n)         | 29.8 | 29.1 | 25.8 | 21  | 16.1 | 12.2 | 9.4 | 7.4 |
| Average number of 30-day mortality (n) | 0.7  | 1.5  | 2.6  | 3.2 | 3.2  | 3.1  | 2.8 | 2.6 |

These simulation results suggest that our stopping rule has a low probability of stopping a study when the true 30-day mortality rate is 10% or less, and the probability of stopping a study is high when the true 30-

day mortality rate exceeds 10%. There, we believe that our stopping rule for 30-day mortality has satisfactory statistical properties.

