#### **10.0 ADVERSE EVENT REPORTING**

##### **10.1 DEFINITIONS**

*Adverse events:* Any untoward medical occurrence in a human subject, including any abnormal sign (e.g., abnormal physical exam or laboratory finding), symptom, or disease, temporally associated with the subject's participation in the research, whether or not considered related to the subject's participation in the research.

This will include:

- Expected events related to the subject's disease process during active enrollment in the research protocol and do not directly result from use of the investigational device or study.
- Procedural events directly related to the cardiac catheterization procedure and recovery from the procedure and do not directly result from use of the investigational device.

*Serious Adverse Event (SAE):* A serious adverse event that results in any of the following and NOT directly related to the device. This includes any event that

- Results in death
- Is life-threatening (places the subject at immediate risk of death from the event as it occurs);
- results in in-patient hospitalization or prolongation of existing hospitalization;
- results in a persistent or significant incapacity;
- results in a congenital anomaly/birth defect (not relevant to this study); or
- based upon appropriate medical judgment, may jeopardize the subject's health and may require medical or surgical intervention to prevent one of the other outcomes listed in this definition.

*Adverse Device Effect (ADE):* Any untoward or unintended response to a medical device. This definition includes any event resulting from insufficiencies or inadequacies in the instructions for use or the deployment of the device or any event that is a result of user error.

During this clinical investigation an event should be considered related to the device when it is the result of:

- Transcatheter Mitral Cerclage Annuloplasty procedure
- Transcatheter Mitral Cerclage Annuloplasty device

An event will be considered NOT related to the Transcatheter Mitral Cerclage Annuloplasty procedure when it is the result of a pre-existing medical condition.

*Anticipated Adverse Device Effects (AADEs):* An AADE is an adverse event with a reasonable possibility that the device or procedure caused or contributed to the event. The following AADEs are considered anticipated based on judgement and clinical experience:

- Death

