| Unanticipated Adverse Device Effects (UADE)                     | As soon as possible but within 10 working days.
Within 7 days (CD)   | FDA; IRB;
CD  |
| Anticipated Adverse Device effect (ADE)                         | Annual summary  | FDA; IRB         |
| Serious Adverse Events (SAE-not directly related to the device) | Annual progress report;
Within 14 days (CD)  | IRB; FDA
CD;  |
| Adverse Events  | Annual summary  | IRB; CD; FDA     |
| Death   | Possibly related to research: within 24 hours of ascertainment otherwise within 7 days (CD)
Annual Progress Report | CD;
IRB; FDA  |
| Unanticipated Problems (UP) involving subject risk              | Within 7 days (CD) otherwise 10 days  | IRB; CD          |
| Major Protocol Deviations (PD)                                  | Annual progress report
Within 7 days (CD)  | FDA; IRB;
CD  |
| Minor Protocol Deviations (PD)                                  | Annual progress report;
Within 14 days(CD)   | FDA; IRB;
CD; |

|   |  |                   |
|---|--|-------------------|
| Serious or Continuing Non-compliance  | Within 10 days
Within 7 days (CD)   | IRB;
CD        |
| Informed consent (use of a device without obtaining informed consent)                         | Within 5 working days  | FDA               |
| Withdrawal of IRB approval  | Within 5 working days  | FDA; IRB; All PIs |
| Withdrawal of FDA approval  | Within 5 working days  | All PIs; IRB      |
| New information that might affect willingness of subjects to enroll or continue participation | Within 7 days  | CD                |
| Recall and Device disposition   | Within 30 working days   | All PIs; IRB; FDA |
| Sponsor suspend or terminate protocol   | If UADE increases risk to subjects, 5 days after determination and $\leq$ 15 working days after sponsor first notified | All PIs; IRB; FDA |
| Final Report (enrollment complete & termination)  | Within 30 working days (termination)
Within 6 months (final report)   | FDA;              |

Abbreviations: CD = NHLBI Clinical Director. FDA = United States Food and Drug Administration; IRB = Institutional Review Board; PI = Principal Investigator

All other adverse events are reported collectively at time of IRB continuing review.

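### The section 9.9 performance table assumes a boundary check after every subject, but the DSMB reviews six-monthly and has no stated expedited route for a 30-day death unless it qualifies as a UADE

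*Combined protocol and SAP*

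**What the plan says.** **The rule (section 9.9).** "The stopping boundary is reached if the posterior probability that the 30-day mortality rate exceeds 10% is at least 85" per cent. "This gives the prior parameters" a = 0.6 and b = 5.4. The table headed "Stop if the number of deaths within 30 days reaches" covers every count from 2 to 30: 2 deaths for 2-5 subjects, 3 for 6-12, 4 for 13-20, 5 for 21-28 and 6 for 28-30. Performance was simulated: each run generated outcomes and "compared these outcomes with the above stopping boundary to determine whether the study was stopped". The text does not say how often the boundary was checked in the simulation, or who checks it in the trial.

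**The board (sections 9.8 and 14.2.3).** The DSMB uses the rule as guidance. "The NHLBI DSMB will review the protocol progress report at six-month intervals"; section 14.2.3 says six and twelve months. The one expedited item is: "Unanticipated Adverse Device Effects (UADEs) will be submitted to the DSMB following the same timelines as the IRB".

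**How deaths are classed and reported (sections 10.1 and 10.2.4).** Death is the first item under "The following AADEs are considered anticipated based on judgement and clinical experience". The site reports a death to the sponsor within 3 working days. The NIH Principal Investigator reports it to the NHLBI Clinical Director "within 24 hours of ascertainment otherwise within 7 days (CD"), the shorter limit applying if it is possibly related to the research, and to the IRB and FDA in the annual progress report. No death row names the DSMB.

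**The concern.** The boundary is the study's only quantitative safety rule, and section 9.9 judges its properties satisfactory on the strength of the simulated table. Those properties belong to a rule checked as each outcome arrives. The board meant to use it is scheduled to look twice a year, and the event the rule counts is not on the list of things sent to it in between. If nobody else applies the boundary, a crossing just after a meeting could wait up to six months while further subjects are treated.

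A crossing can also disappear. Three deaths in 12 subjects meets the boundary; three in 13 does not. Sparse looks therefore lower the chance of stopping as well as delaying it.

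**Working it through.** **Step 1: the boundary.** With s deaths in n subjects, the posterior is Beta(0.6 + s, 5.4 + n - s). Stop when P(rate > 0.10) is at least 0.85. The prior carries 0.6 + 5.4 = 6 subjects' weight, and 6/30 = 20%, the stated weight for a 30-subject trial. Tail probabilities where the printed rows change:

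- s = 2: 0.875 at n = 5, 0.8475 at n = 6
- s = 3: 0.8697 at n = 12, 0.849 at n = 13
- s = 4: 0.8572 at n = 20, 0.8398 at n = 21
- s = 5: 0.8525 at n = 28, 0.8372 at n = 29

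The printed boundary is reproduced, with 5 deaths at n = 28.

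**Step 2: the look schedule behind the performance table.** Let f_n(k) be the probability of k deaths after n subjects without having stopped. Then f_n(k) = (1 - p) f_(n-1)(k) + p f_(n-1)(k - 1). At each look, the mass at or above the boundary is removed and counted as stopped. Mean subjects is the sum of n times the mass removed at n, plus 30 times what remains.

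| True mortality | 10% | 15% | 20% | 25% | 30% |
|---|---|---|---|---|---|
| Printed, % stopped | 24 | 52 | 76 | 90 | 97 |
| N = 30, look after each subject | 23.7 | 51.8 | 75.9 | 90.2 | 96.8 |
| Printed, mean subjects | 25.8 | 21 | 16.1 | 12.2 | 9.4 |
| N = 30, look after each subject | 25.8 | 21.0 | 16.2 | 12.2 | 9.4 |

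The alternatives fail. Looks every 2 subjects give a mean of 17.0 at 20% mortality. Looks every 5 give 72.0% stopped and a mean of 17.8. The 15 trials named in the text give 15.2% stopped at 10% and 51.1% at 20%. The printed table is therefore N = 30 with a look after every subject.

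**Step 3: six-monthly looks.** Accrual is an assumption. The version history dates the interactive IDE review February 2019 and Amendment F July 2020, about 17 months apart, and Amendment F refers to the first 10 subjects. That gives 10/17 = 0.59 a month, or 30/0.59 = about 51 months for 30 subjects. Faster cases are shown as a range.

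The calendar simulation used 20,000 runs per setting, Poisson accrual, a random phase for the first meeting, deaths uniform over 30 days, survivors counted at day 30, and a final look after the last outcome.

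| | Printed | 51 mo (0.59/mo) | 36 mo (0.83/mo) | 24 mo (1.25/mo) | 18 mo (1.67/mo) |
|---|---|---|---|---|---|
| % stopped, 10% mortality | 24 | 20.1 | 18.9 | 17.3 | 16.2 |
| % stopped, 20% | 76 | 71.8 | 70.8 | 69.6 | 68.2 |
| % stopped, 30% | 97 | 96.1 | 95.6 | 95.2 | 95.0 |
| Mean treated, 20% | 16.1 | 18.7 | 19.5 | 20.6 | 21.6 |
| Mean treated, 30% | 9.4 | 11.9 | 12.9 | 14.5 | 15.8 |
| Mean deaths, 20% | 3.2 | 3.7 | 3.9 | 4.1 | 4.3 |
| Mean deaths, 30% | 2.8 | 3.6 | 3.9 | 4.3 | 4.7 |

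Calibration: checked at every outcome instead, the 51-month simulation gives 24.9%, 75.9% and 96.7% stopped at 10%, 20% and 30%, close to the printed values. As a rough check on the excess, an average wait of 3 months at 0.59 a month is 1.8 subjects before allowing for crossings that lapse. The simulated excess at 20% is 18.7 - 16.1 = 2.6.

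**Step 4: the route to the DSMB.** The rule counts all deaths within 30 days. Under section 10.1, a death not related to the device is a serious adverse event and falls outside the UADE definition. A device-related death is on the anticipated list and becomes a UADE only if its nature, severity or degree of incidence was not previously identified. Excess incidence is what the boundary is meant to detect, so that limb cannot be relied on to bring the first deaths to the board.

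**The case against.** Four points on the other side have force.

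First, a reader might infer that no death can reach the DSMB between meetings. The documents do not support that. A death unanticipated in nature, severity or incidence is a UADE and is sent to the board, and section 9.8 does not bar other communication.

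Second, a reader might infer that the printed table is wrong for this trial. Section 9.9 is silent on who checks and when. A check at each outcome followed by referral to the DSMB would fit its wording, and the table would then hold. What is missing is any sentence that assigns that check.

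Third, other safeguards act quickly. Every death prompts an unreasonable-risk determination by the sponsor and the NIH Principal Investigator, with termination within 5 to 15 working days if affirmative (9.8). That investigator monitors continuously (14.2.1). FDA receives 30-day data for each five subjects (10.2.5). An independent committee adjudicates first-year deaths (9.6). These reduce the practical risk. None is tied to the boundary, and section 14.1 makes the NIH Principal Investigator the sponsor representative, so the determination is not independent of the sponsor.

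Fourth, the rule is guidance in a small descriptive feasibility study with no acceptance criteria. This limits the consequences for the analysis, but not the value of the rule as protection.

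One tempting comparison should be avoided. Counting only stops made before all 30 subjects are treated gives about 62-71% at 20% mortality for accrual of 0.6 to 1.5 a month. The printed 76% includes crossings up to and including subject 30, so the two are not like for like.

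**Conclusion.** The point stands in a limited form. The performance table describes a boundary checked after every subject, as reproduction shows although the text does not say so. The plan schedules the DSMB six-monthly, gives a 30-day death no stated expedited route to it unless the death is a UADE, and assigns the boundary check between meetings to nobody.

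If the boundary is applied only at six-month reviews, the loss in stopping probability against the printed table is about 4 to 8 points at 10% and 20% mortality, and about 1 to 2 points at 30%. At the pace suggested by the first ten subjects, about 2.5 more subjects are treated on average at 20% and 30% mortality, with about 0.5 and 0.8 more deaths respectively. At an assumed 1.5 a month, about 68-69% stop at 20% mortality with about 21-22 treated.

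The sizes rest on assumed accrual, no enrolment pause after a death, and no use of the boundary between meetings. The effect is modest at slow accrual. The gap in the reporting route does not depend on those assumptions.

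**What to change.** In sections 9.8 and 10.2.4, name the DSMB as a recipient of every death within 30 days of an attempted procedure, whether or not anticipated or device-related, on the clock already used for the Clinical Director. State in section 9.9 that the boundary is checked at each such death, and by whom. The printed table then describes the monitoring to a close approximation.

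If six-monthly checking is preferred, re-run the simulation for that schedule with a stated accrual rate and replace the table.

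The same edit should reconcile the review intervals in 9.8 and 14.2.3, correct the 15 simulated trials to match the 30-subject table, remove n = 28 from one of its two boundary rows (the stated criterion gives 5 deaths there), and repair the pointer in 9.8 to a section 9.2.4 that does not exist (the timeframes are in 10.2.4).

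The cost is a few sentences, one table entry and a short ad hoc DSMB communication per death. The printed table implies an average of about 1 to 3 such deaths.

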## 9.9 STOPPING RULES

The study will be monitored to ensure that the mortality within 30-days after the procedure does not substantially exceed an anticipated rate. We anticipate the rate of 30-day mortality is 10% or less and determine the stopping rule by a Bayesian approach . The stopping boundary is reached if the posterior probability that the 30-day mortality rate exceeds 10% is at least 85%. We take our prior distribution to be a beta distribution so that our prior clinical opinion is worth 20% of the weight we will place on the new data. This gives the prior parameters  $a = 0.6$ ,  $b = 5.4$ . Hence when we make decisions about stopping the study, the data from the study will dominate over the prior opinion.

The following table summarizes the threshold numbers for the stop rule boundary, which may lead to a recommendation to stop the study due to the excess 30-day mortality.

| Number of subjects | Stop if the number of deaths within 30 days reaches |
|--------------------|---|
| 2-5                | 2   |
| 6-12               | 3   |
| 13-20              | 4   |
| 21-28              | 5   |
| 28-30              | 6   |

We investigated the performance of the above stopping rule by a simulation study. In each simulation run, we generated a study with 15 independent Bernoulli trials, each with a true certain 30-day mortality, and compared these outcomes with the above stopping boundary to determine whether the study was stopped. We repeated the simulation 100,000 times and computed the proportion of stopped studies using the above stopping rule. The following table summarizes the performance of this stopping rule:

| True 30-day mortality rate             | 2.5% | 5%   | 10%  | 15% | 20%  | 25%  | 30% | 35% |
|--|------|------|------|-----|------|------|-----|-----|
| Proportion of Stopped Studies (%)      | 1    | 4    | 24   | 52  | 76   | 90   | 97  | 99  |
| Average number of subjects (n)         | 29.8 | 29.1 | 25.8 | 21  | 16.1 | 12.2 | 9.4 | 7.4 |
| Average number of 30-day mortality (n) | 0.7  | 1.5  | 2.6  | 3.2 | 3.2  | 3.1  | 2.8 | 2.6 |

These simulation results suggest that our stopping rule has a low probability of stopping a study when the true 30-day mortality rate is 10% or less, and the probability of stopping a study is high when the true 30-

day mortality rate exceeds 10%. There, we believe that our stopping rule for 30-day mortality has satisfactory statistical properties.

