## 9.0 BIOSTATISTICAL AND ANALYTICAL CONSIDERATIONS

### 9.1 SAMPLE SIZE

This is an early feasibility study of a device not previously used in humans. An arbitrary initial sample size of 30 is proposed in coordination with the FDA Centers for Devices and Radiologic Health, which is increased from 15 in Amendment A

Up to 60 subjects will be consented until 30 subjects undergo attempted Transcatheter Mitral Cerclage Annuloplasty total in this protocol.

We will adhere to the extent possible to consensus guidelines that have been established for the analysis and reporting of transcatheter mitral valve repair investigational procedures (MVARC).

There are no prespecified acceptance criteria for failure rate.

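### Section 9.9 gives two stopping thresholds at 28 subjects, describes its simulation with 15 subjects instead of 30, and claims a separation at 10% mortality that its own table does not show

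*Combined protocol and SAP*

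**What the plan says.** Section 9.9 (Stopping rules) sets the mortality criterion: "The stopping boundary is reached if the posterior probability that the 30-day mortality rate exceeds 10% is at least 85" per cent. The prior is Beta(0.6, 5.4), chosen so that "our prior clinical opinion is worth 20% of the weight we will place on the new data".

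The boundary table asks for 2 deaths at 2-5 subjects, 3 at 6-12, 4 at 13-20, 5 at 21-28 and 6 at 28-30.

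On the rule's performance, the section says that in each run "we generated a study with 15 independent Bernoulli trials". At true rates of 2.5, 5, 10, 15, 20, 25, 30 and 35% it then reports:

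- studies stopped: 1, 4, 24, 52, 76, 90, 97 and 99%;
- mean number of subjects: 29.8, 29.1, 25.8, 21, 16.1, 12.2, 9.4 and 7.4.

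It concludes that "our stopping rule has a low probability of stopping a study when the true 30-day mortality rate is 10% or less", that "the probability of stopping a study is high when the true" rate exceeds 10%, and that the rule's properties are therefore satisfactory.

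Section 9.1 (Sample size) plans to enrol "until 30 subjects undergo attempted Transcatheter Mitral Cerclage Annuloplasty", a number "which is increased from 15 in Amendment A". Section 9.8 has the DSMB "using proposed Stopping Rules (section 9.9) as a guidance".

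**The concern.** This is the trial's only quantitative mortality boundary, and three pieces of text around it do not agree with its numbers.

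- **Two thresholds at 28.** Someone holding 5 deaths in 28 subjects finds one row that says the boundary is reached and another that says it is not.
- **Simulation size.** A study of 15 subjects cannot have a mean of 29.8 subjects, so the described simulation cannot have produced the table.
- **Closing claim.** It is the stated basis for calling the rule satisfactory. It tells an IRB, a DSMB or a regulator that the rule separates acceptable from unacceptable mortality at 10%. The table directly above it shows a gradual rise through that region.

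**Working it through.** **Inputs (all from section 9.9 unless noted).** Prior Beta(0.6, 5.4); stop when P(rate > 0.10 | data) is at least 0.85; the printed boundary; 100,000 simulation runs; planned N = 30 (section 9.1).

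**Step 1: the boundary.** With d deaths in n subjects the posterior is Beta(0.6 + d, 5.4 + n − d). For each n, take the smallest d whose posterior probability above 0.10 is at least 0.85. The result is 2 (n = 2-5), 3 (6-12), 4 (13-20), 5 (21-28) and 6 (29-30). This matches the printed table everywhere except the lower end of the last row. Around the overlap:

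| Data | P(rate > 10%) | Criterion met? |
|---|---|---|
| 5 of 27 | 0.8670 | yes |
| 5 of 28 | 0.8525 | yes |
| 5 of 29 | 0.8372 | no |
| 5 of 30 | 0.8214 | no |

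**Step 2: the operating table.** I followed the binomial death count exactly, applying the boundary after every subject. Studies stopped (%):

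| True rate | Printed | N=30, 5 at n=28 | N=30, 6 at n=28 | N=15 |
|---|---|---|---|---|
| 2.5% | 1 | 0.86 | 0.85 | 0.78 |
| 5% | 4 | 4.53 | 4.44 | 3.52 |
| 10% | 24 | 23.69 | 22.94 | 15.16 |
| 15% | 52 | 51.85 | 50.49 | 32.46 |
| 20% | 76 | 75.86 | 74.60 | 51.13 |
| 25% | 90 | 90.21 | 89.45 | 67.73 |
| 30% | 97 | 96.75 | 96.41 | 80.53 |
| 35% | 99 | 99.12 | 99.00 | 89.28 |

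With N = 30 and 5 deaths at n = 28, the exact mean number of subjects is 29.80, 29.08, 25.82, 21.00, 16.15, 12.22, 9.37 and 7.40, which agrees with the printed row to rounding and simulation error. With N = 15 it runs from 14.93 down to 6.81.

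**Step 3: which value at n = 28 was simulated?** The simulation standard error is √(p(1−p)/100,000), at most 0.16 points. The cells at 10, 15 and 20% decide. For the 6-death version to print as 24, 52 and 76 it would have to reach 23.5, 51.5 and 75.5; it falls short by 0.56, 1.01 and 0.90 points, more than four standard errors each time. At 25% and 30% the 6-death values lie within two standard errors of the rounding point, so those cells say little. At 5% the printed 4 fits 4.44 slightly better than 4.53, but 4.53 is only 0.03 above the rounding point against a standard error of 0.07.

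**Step 4: prior weight.** 0.6 + 5.4 = 6. Then 6/30 = 20%, as stated, whereas 6/15 = 40%. The prior, like the table, belongs to 30 subjects.

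**Step 5: the closing claim.** Exact stopping probabilities between the tabulated rates:

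| True rate | 10% | 11% | 12% | 13% | 14% | 15% |
|---|---|---|---|---|---|---|
| Stopped (%) | 23.7 | 29.1 | 34.7 | 40.4 | 46.2 | 51.9 |

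Stopping passes 10% at a true rate of 6.9%, 50% at 14.7% and 80% at 21.1%.

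**Step 6: size of the overlap.** The chance of first reaching the boundary exactly at n = 28 is 0.9, 1.9 and 2.0% at true rates of 10, 15 and 20%. Using 6 instead of 5 there lowers overall stopping by 0.75, 1.36 and 1.26 points at those rates, and by at most 1.40 points (at 16.7%). The shift is smaller than the first-reach chance because some of those studies reach 6 deaths at n = 29 or 30.

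**The case against.** The strongest reply is that this is editorial. The table is correct and is printed just above the sentence at issue, so nothing is hidden. Low and high are given no numeric meaning, and no rule with 30 subjects could switch from one to the other at 10%. Section 9.9 also states its aim as detecting mortality substantially above the anticipated rate, and from 20% up the rule stops 76% or more. The row overlap is settled by the written criterion, and the 15 is a leftover from before Amendment A that a careful reader would correct. The rule is guidance, and section 9.8 separately requires a risk determination after every death.

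Much of this stands. The consequences are modest, and whether 24% at exactly 10% counts as low is partly judgement. What does not stand is the claim of a high stopping probability above 10%. A probability of 35% at 12%, or 52% at 15%, is not high on any ordinary reading. That sentence asserts a property the rule lacks, and the verdict of satisfactory properties is drawn from it. Guidance still needs one threshold for each number of subjects.

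**Conclusion.** All three points hold. The boundary criterion and the operating table are sound for N = 30; the text around them is not.

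- The duplicated n = 28 is a genuine contradiction with a small effect, and the plan's own criterion resolves it.
- The simulation size of 15 is wrong as written, but correcting it changes no tabulated figure.
- The closing claim is supported at 2.5% and 5% and from 20% up. It is not supported at 15%, and only doubtfully at 10%.

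The stopping figures assume independent outcomes and a check after every subject with 30-day status known. That reading reproduces the plan's own table.

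**What to change.** Three edits in section 9.9:

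1. Reconcile the last two boundary rows with the written 85% criterion, which yields 21-28 (5 deaths) and 29-30 (6 deaths).
2. Change the simulated study size from 15 to 30 and leave the operating table as printed.
3. Replace the closing low/high sentence with the figures: the rule stops about 1% of studies at a true 30-day mortality of 2.5%, 4-5% at 5%, 24% at 10%, 52% at 15%, 76% at 20% and at least 90% from 25% up, assuming the boundary is checked after every subject. Qualify the statement about satisfactory properties to match. Naming who makes that check would be a useful but optional addition.

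The cost is wording in one section. No patients, tests, criterion values or new simulations are needed. The stated properties will read slightly less favourably.
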